2.2 Subject Population

2.2.1 Sample Size Justification

Sample size was calculated using the 2-sample means statement in the POWER procedure in SAS. A sample size of 45 subjects per treatment group will provide 80% power to detect a 1.2-point difference in the change from Baseline pain score

between AQX-1125 and placebo assuming a between-subject standard deviation of 2.0 and a 2-sided 5% significance level.

Assuming a 10% rate of discontinuation from study drug, the total number of subjects to be randomized is approximately 100. Subjects who discontinue will be included in the primary analysis, resulting in a slight decrease in power if the discontinuing subjects in the placebo group have no additional change after discontinuation of study drug while the discontinuing subjects in the AQX-1125 group have a loss of efficacy after discontinuing study drug.

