2.2.4 Randomization/Unblinding

2.2.4.1 Randomization Methodology

Approximately 100 male subjects with diagnosed CP/CPPS will be randomized to either AQX 1125 (200 mg) or placebo in a 1:1 ratio.

A central, permuted block randomization scheme will be used with a selected blocking factor (block size) determined based on the proposed allocation ratio and number of subjects. The block size will be specified in the randomization plan.

An Interactive Web Response System (IWRS) will be used for the randomization to either AQX-1125 (200 mg) or placebo and subsequent wallet assignments. Study staff will log in to the IWRS using unique credentials and input subject-specific screening and baseline information. In accordance with the randomization schedule, the IWRS will assign the randomization number and unique wallet numbers to the subject. Each subject must be given only the wallets assigned by IWRS. The study staff will document the wallet number in the Study Drug Accountability electronic Case Report Form (eCRF). Subjects are to be randomized in the order in which they qualify from the screening phase for inclusion in the study. The randomization plan will be executed in accordance with CTDS' SOP DM016: Generation of Randomization Schemes/Unblinding.

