The MMRM model to assess time course will have treatment as a factor, the corresponding baseline value as a covariate, a linear term for time (in weeks), and a time×treatment interaction effect term. The model will allow for a subject random intercept and slope over time with an unstructured correlation matrix. Sample SAS code for the time course MMRM is provided in Appendix B – Sample MMRM Code.

For response to treatment as measured by the GRA and PGI-C at Week 12 (Visit 4), the frequency distribution of each response scale will be presented by treatment group and assessed using a chi-square row mean score difference test.

- The GRA response is a 7-point Likert scale (range: -3 to 3) with a score of -3 indicating “Markedly Worse”, a score of 0 indicating “No Change”, and a score of 3 indicating “Markedly Improved” to the question: *As compared to when you started the study drug, how would you rate your Chronic Prostatitis / Chronic Pelvic Pain Syndrome symptoms now?*
- The PGI-C response is a 7-point Likert scale (range: 1 to 7) with a score of 1 indicating “Very much improved”, a score of 4 indicating “No change”, and a score of 7 indicating “Very much worse” to the item: *Choose the response that best describes the overall change your pelvic pain since you started the study.*
- The PGI-S response is a 5-point ordinal scale with a score of 1 being “None” and a score of 5 being “Very Severe” to the item: *Choose the response that best described the severity of your chronic prostatitis / chronic pelvic pain symptoms over the past week.*

For response to treatment as measured by the PGI-S at Week 12 (Visit 4), the frequency distribution of each response scale will be presented by treatment group and the change from baseline will be assessed by an ANCOVA model with treatment as a factor and baseline PGI-S as a covariate.

For the following two dichotomous secondary efficacy endpoints the rates for each treatment group and difference between the treatment groups will be presented with corresponding 95% CIs. A CMH test will be used to test for differences in rates between the treatment groups controlling for baseline pelvic pain. The baseline pelvic pain will be stratified into 2 categories (4-7 and >7):

- (1) Treatment response as defined by meeting either of the following:

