 - Decrease in maximum daily pelvic pain (mean) from Baseline to Week 12 using a standardized 11-point NRS with no change in the amount or strength of concomitant analgesic medications (as defined in Section 2.2.14).
 - Decrease in maximum daily pelvic pain from Baseline to Week 12 using a standardized 11-point NRS with a decrease in the amount or strength of concomitant analgesic medications (as defined in Section 2.2.14).
- (2) A $\geq 30\%$ and $\geq 50\%$ improvement (decrease) in maximum daily pelvic pain (mean) (using the 11-point NRS recorded by eDiary and the NIH-CPSI pain subscale), at Weeks 6 (Visit 3) and 12 (Visit 4).

For the Discontinuation of study medication due to treatment failure endpoint, only summary statistics will be provided for the percent meeting treatment failure criteria and the time to event (no inferential analyses will be performed). Time to discontinuation of study medication due to treatment failure will be summarized and presented graphically using Kaplan-Meier methods (i.e., SAS PROC LIFETEST stratifying on treatment group).

The frequency distribution of the 5-category IIEF-EF score will be presented by treatment group for Week 12 as well as a shift table from Baseline. The 5 categories are no erectile dysfunction (score: 26-30), mild erectile dysfunction (score: 22-25), mild to moderate erectile dysfunction (score: 17-21), moderate erectile dysfunction (score: 11-16) and severe erectile dysfunction (score: 1-10). Responses to all items must be completed to calculate an IIEF-EF score. Any response with missing values will be excluded from the analyses. Treatment group difference

with corresponding 95% CIs in the 5-category IIEF-EF will be assessed by a Cochran-Mantel-Haenszel (CMH) test using row mean scores controlling for Baseline IIEF-EF score.

Data from both treatment arms will be used to calculate a meaningful change threshold (MCT), which reports a change in the primary endpoint (change in maximum daily pelvic pain) by anchoring to other outcomes (including PGI-S and/or PGI-C) to determine a change in maximum pelvic pain that provides a meaningful benefit to patients. The determination of the MCT will be made outside of the methods documented in this SAP prior to database lock. Once the MCT is determined, the proportion of subjects who have an improvement of at least the MCT will be summarized by treatment group and compared using a chi-square test as an exploratory analysis.

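### The meaningful-change responder comparison uses an unadjusted chi-square test, although the other responder cuts of the same pain change are tested with baseline pain controlled

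*SAP*

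**What the plan says.** SAP 2.2.13.3 (Secondary Endpoints) uses different tests for outcomes that lie close together:

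- **MCT responder.** The threshold is an absolute change in maximum daily pelvic pain, set by anchoring to PGI-S and/or PGI-C. The proportions reaching it are "compared using a chi-square test as an exploratory analysis".
- **Other responder endpoints** (pain decrease combined with analgesic use; at least 30% and 50% improvement). For these, "A CMH test will be used to test for differences in rates between the treatment groups controlling for baseline pelvic pain". The strata are 4-7 and above 7.
- **GRA and PGI-C at Week 12.** These are "assessed using a chi-square row mean score difference test", with no baseline term. Protocol 10.4.2.5 also names a chi-square test for them.
- **Scales with their own baseline.** PGI-S is adjusted for baseline PGI-S, and the IIEF-EF categories for baseline IIEF-EF.

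The primary mixed model (SAP 2.2.13.1) has baseline NRS score as a covariate. Randomization (SAP 2.2.4.1) is by central permuted blocks with no stratification factor named. SAP 2.2.13.3 makes all secondary P values descriptive, and Protocol 10.4.2.6 does not control error for them.

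**The concern.** The MCT responder and the 30%/50% eDiary responders are dichotomies of one variable, the change in maximum daily pelvic pain. One is tested without regard to baseline and the others with it. A reader who sees them in adjacent tables could not tell whether a difference in P value came from the threshold or from the adjustment.

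An absolute threshold is also sensitive to baseline. A man who starts higher has more room to fall and regresses further toward the mean. With about 50 men per arm and no stratification by pain, a chance difference in baseline would pass into the MCT comparison uncorrected. At stake are consistency and a small amount of precision in an exploratory analysis, not the trial's main conclusion.

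**Working it through.** **1. The plan's own figure.** SAP 2.2.1: "A sample size of 45 subjects per treatment group will provide 80% power to detect a 1.2-point difference" "assuming a between-subject standard deviation of 2.0 and a 2-sided 5% significance level". The standardized effect is 1.2/2.0 = 0.6, the noncentrality is 0.6 × √(45/2) = 2.85, and there are 88 degrees of freedom. The noncentral t gives 80.4% power, so the stated 80% reproduces. "Assuming a 10% rate of discontinuation from study drug, the total number of subjects to be randomized is approximately 100": 90/0.90 = 100, which also reproduces. These figures are for the primary endpoint. The documents give none for the MCT, GRA or PGI-C.

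**2. Does the MCT outcome depend on baseline?** Let ρ be the correlation of baseline with Week 12 maximum pain. The correlation of change with baseline is

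(ρ·SD₁₂ − SD_b) / √(SD_b² + SD₁₂² − 2ρ·SD_b·SD₁₂).

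The documents give neither ρ nor the two SDs. Assume SD_b = 1.4 and SD₁₂ = 2.05.

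| ρ | numerator | SD of change | correlation of change with baseline |
|---|---|---|---|
| 0.3 | 0.615 − 1.4 = −0.785 | √4.44 = 2.11 | −0.37 |
| 0.5 | 1.025 − 1.4 = −0.375 | √3.29 = 1.81 | −0.21 |
| 0.65 | 1.333 − 1.4 = −0.068 | √2.43 = 1.56 | −0.04 |

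The dependence vanishes only at ρ = 1.4/2.05 = 0.68. Under these SDs, the design's change SD of 2.0 corresponds to ρ = (6.16 − 4.00)/5.74 = 0.38.

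**3. Chance imbalance.** With 45 per arm and SD_b = 1.4, the standard error of the baseline difference is 1.4 × √(2/45) = 0.30. A difference above 0.3 points in either direction therefore occurs in about 3 trials in 10. The slope of change on baseline is ρ·SD₁₂/SD_b − 1, which is −0.56 at ρ = 0.3 and −0.27 at ρ = 0.5. An imbalance of 0.3 moves the mean difference in change by about 0.17 or 0.08 points, against a design effect of 1.2.

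**4. Power for the MCT responder.** Simulation assumptions: 45 analysed per arm; baseline mean 6.5, SD 1.4, clipped to 4-10; mean placebo change −1.0; treatment effect −1.2; thresholds 1.5, 2 and 3 points; 20,000 trials per setting.

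| ρ | change in power, two-stratum CMH minus chi-square (percentage points) |
|---|---|
| 0.3 | +0.5 to +3.4 |
| 0.5 | −1.4 to +1.2 |
| 0.65 | −2.0 to +0.3 |

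In a smaller run (1,500 trials, Monte Carlo standard error about 1.3 points) with a 2-point threshold, power went from about 57% to 60% at ρ = 0.3 and from 67% to 68% at ρ = 0.5. The negative values occur mainly at the 3-point threshold. There the plain chi-square test rejects a true null in about 5.4% to 5.9% of trials, against about 5% for CMH, so much of that apparent loss is excess type I error.

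A separate simulation, with assumed response rates of 24% and 46% and 40,000 trials per setting, set the correlation r between baseline and the underlying outcome directly. Power went from 58.1% to 58.3% at r = 0, from 58.1% to 59.9% at r = 0.3, and from 58.1% to 62.8% at r = 0.5. The sizes of correlation in step 2 for ρ of 0.3 and 0.5 (0.37 and 0.21) lie between r = 0.2 and r = 0.4, where the gain is about 1 to 3 points.

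**5. GRA and PGI-C.** The second simulation also covered a seven-category score with a 0.6 SD latent effect and 30% of men in the upper stratum.

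| r | unadjusted | row-mean-score CMH, two strata |
|---|---|---|
| 0 | 77.6% | 77.1% |
| 0.2 | 77.9% | 78.3% |
| 0.3 | 77.8% | 79.3% |
| 0.5 | 77.6% | 82.8% |

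The documents do not say which row applies. Type I error was near 5% for both tests.

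**The case against.** The strongest reply is that nothing depends on these P values. The MCT comparison is exploratory, the secondary P values are descriptive, and randomization has no stratification factor that the analysis must carry. The primary model already adjusts the underlying pain change for baseline. All of this stands, and it limits the point to a minor one.

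A second reply is that stratifying can cost power. The simulated losses reach about 2 points, at ρ = 0.65 with the 3-point threshold. That setting implies a change SD of about 1.6, below the design's 2.0, and part of the loss reflects the slightly liberal chi-square test. It is a weak argument against the change, but it does rule out promising a gain.

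A reader might infer that GRA and PGI-C are equally inconsistent and that all three tests certainly give up precision. The documents do not support this. GRA and PGI-C are seven-category ratings of change, not responder endpoints. They are first collected at Visit 3 and have no baseline of their own. The SAP follows a recognizable pattern of adjusting a scale for its own baseline where one exists. GRA also rates CP/CPPS symptoms as a whole, not pain alone. Whether either rating correlates with baseline pain is not reported, and if it does not, there is nothing to recover.

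**Conclusion.** The inconsistency is real for the MCT responder. It is a cut of a variable that the primary model adjusts for baseline, and its sibling responder endpoints are tested with baseline pain controlled. Correcting it buys consistency, protection against chance imbalance, and a power change from about nil to about 3 points. That range rests on assumed SDs of 1.4 and 2.05, a two-stratum split at 7, thresholds of 1.5 to 3 points, and an unknown baseline-to-Week-12 correlation.

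It would be wrong to infer that the unadjusted test is invalid. Its type I error is close to nominal, and no success criterion uses it. For GRA and PGI-C, adjustment is optional. This is a worthwhile tidy-up of low severity.

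**What to change.** Before unblinding, which SAP 2.2.12 places after the interim lock at Week 16, replace the chi-square test for the MCT responder with the CMH test already planned for the other responder endpoints. State that the strata are formed from baseline maximum daily pelvic pain. The SAP's present term does not say whether average or maximum pain is meant, so the same sentence should settle this for the existing CMH tests too.

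CMH is preferable here to logistic regression on continuous baseline. Logistic regression would report a conditional odds ratio, while the other responder endpoints are reported as rates and rate differences.

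Optionally, test GRA and PGI-C with the row-mean-score CMH test in the same strata, recording this as a departure from the chi-square test in Protocol 10.4.2.5. Otherwise leave them as they are.

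The cost for the MCT is a sentence of SAP text and a small change to the code. No new data are needed.

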9.2.6 Patient's Global Impression of Severity Scale

Assessment of the subject's current symptoms will be performed by the subject using a 5-item scale ([Appendix 8. Patient's Global Impression of Severity Scale](#)). This information will be collected at Visits 2, 3, 4, ET (if needed), and at the Off-Treatment Safety Follow-up Visit.

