2.2.10.2 Imputation Methods

The primary endpoint analysis method is a mixed model for repeated measures (MMRM) ANCOVA. This is an observed case approach to missing data and assumes the missing data is missing at random (MAR).

Sensitivity analyses for the primary efficacy analysis will include imputing the missing data using two multiple imputation (MI) methods (described below). Any sensitivity analyses performed will be considered supportive analysis.

- Multiple Imputation Assuming Missing at Random: Missing post-baseline weekly maximum daily pelvic pain (mean) change from baseline scores at Weeks 6 and 12 will be imputed via MI assuming (MAR). SAS Proc MI using the linear regression method will be the method for the imputation if the missing data pattern follows a monotonic pattern. If the data does not follow a monotonic pattern a sequential approach to imputing the variables to produce a monotone missing data pattern as described in Alut (2012) will be applied.

A default random number generator of 345353 will be used and 100 imputed datasets will be created. Each of the imputed datasets will be analyzed via the same model as the primary efficacy endpoint analysis (See Section 2.2.13.1). The range of the imputed pain values will be set between 0 and 10 via the SAS Proc MI Maximum and Minimum options. The results across the multiple imputed data sets will be combined using SAS Proc MIANALYZE.

The following are the set of variables to be used in the MI model:

- treatment group (placebo/AQX-1125)
- age group (<65, 65-<75, ≥75 years)
- race (White/Non-White)
- baseline daily pelvic pain score
- experienced a severe AE (yes/no) (CTCAE grade 3-5, severe, life-threatening or death)
- duration of exposure [last day-first day] +1

For the ‘experienced a severe AE’ imputation variable, if a subject experiences a severe AE from baseline to Week 6 the value will be ‘yes’ for the imputation of the Week 6 time-point, ‘no’ otherwise. Similarly, if a subject experiences a severe AE from Baseline to Week 12 the value will be ‘yes’ for the imputation of the Week 12 time-point, ‘no’ otherwise.

Note: if the MI model does not converge or produce estimates (i.e., due to over-specification) the set of imputation variables may be modified.

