2.2.13.3 Secondary Endpoints

P values for secondary endpoints will be used for descriptive purposes rather than for statistical inference; therefore, no adjustments for multiplicity will be utilized.

The following four change from Baseline to Week 12 endpoints will be analyzed in a manner similar to the primary efficacy analysis as described in Section 2.2.13.1:

- (1) NIH-CPSI pain subscale (pain, urinary symptoms and quality of life impact) and all domains total score
 - Total score (score range 0-43)
 - Pain: Total of items 1a, 1b, 1c, 2a, 2b, 3, 4 (score range 0-21)
 - Urinary Symptoms: total of items 5 and 6 (score range 0-10)
 - QoL Impact: total of items 7,8 and 9 (score range 0-12)

NIH-CPSI data are collected on a paper form at each planned clinic visit.

- (2) Male sexual health as measured using the International Index of Erectile Function Questionnaire, Erectile Function domain (IIEF-EF): The IIEF-EF score is the sum of the ordinal responses to the 5 items

IIEF-EF data are collected on a paper form at each planned clinic visit.

- (3) Mean of average daily pelvic pain scores (eDiary), average pelvic pain (in clinic), and maximum daily pelvic pain (in clinic).

Average and maximum daily pelvic pain are collected on the eDiary, and also on a paper form at each planned clinic visit. Analysis of data collected on paper at the planned clinic visits will be used to confirm results from the analysis of data collected on the eDiary.

- (4) 24-hour voiding frequency

For each of the scheduled assessment periods, the voiding frequency will be the last 24-hour period in which voiding is collected (i.e., if voiding is collected in more than one 24-hour period).

The following four-time course secondary endpoints will be assessed by MMRM model where the change from Baseline (Visit 2) to Week 6 (Visit 3), Week 12 (Visit 4), and Week 16 (i.e. 4 weeks after end of treatment) is the dependent variable:

- (1) Mean of maximum daily pelvic pain score (eDiary)
- (2) NIH-CPSI pain subscale and all domains total score
- (3) IIEF-EF
- (4) Mean of average daily pelvic pain scores (eDiary), average and maximum pelvic pain (Paper-based NRS in clinic)

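### PGI-S is compared at Week 12 only, so a man with a Week 6 rating but no Week 12 rating leaves the comparison; the two-visit MMRM used for the other scales would keep him

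*SAP*

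**What the plan says.** The PGI-S analysis in SAP 2.2.13.3 is tied to one visit: "For response to treatment as measured by the PGI-S at Week 12 (Visit 4), the frequency distribution of each response scale" is tabulated by arm, and "the change from baseline will be assessed by an ANCOVA model with treatment as a factor and baseline PGI-S as a covariate". The model has no Week 6 term.

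PGI-S is nevertheless measured at Week 6. Protocol 9.2.6 states: "This information will be collected at Visits 2, 3, 4, ET (if needed), and at the Off-Treatment Safety Follow-up Visit". Visit 3 is Week 6.

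The continuous scales are treated differently. SAP 2.2.13.3 says "The following four change from Baseline to Week 12 endpoints will be analyzed in a manner similar to the primary efficacy analysis", and lists NIH-CPSI, IIEF-EF, average daily pain with the in-clinic pain ratings, and voiding frequency. The primary analysis in SAP 2.2.13.1 is an MMRM on change at Weeks 6 and 12.

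No other rule brings back a man without a Week 12 PGI-S:
- The multiple imputation in SAP 2.2.10.2 covers the primary efficacy analysis only.
- SAP 2.1 limits Early Termination assessments to descriptive summary.
- PGI-S is not in the time-course list of SAP 2.2.13.3.

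GRA and PGI-C are also compared at Week 12 only, "assessed using a chi-square row mean score difference test". Protocol 9.2.4 and 9.2.5 collect them at Visits 3 and 4, Early Termination and the off-treatment visit, so neither has a baseline value.

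**The concern.** The overall response on the global scales is a named secondary objective, and ITT is the primary efficacy population. A single-visit ANCOVA with no imputation is an observed-case analysis. It uses every man with a Week 12 rating, including those who stopped drug and still attended, and drops the rest. A man who rates himself severe at Week 6 and then leaves counts in the NIH-CPSI comparison but not in the PGI-S comparison.

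That omission distorts the estimate if leaving is related to the Week 6 rating and the relation or the amount differs by arm. If poorly responding placebo men leave more often, the drug effect is understated; the opposite pattern overstates it. Even without bias, the Week 6 information on those men is discarded and some precision is lost. Estimates matter here because the synopsis would call the study a success, even without significance, if the estimated effect predicts significance in a larger trial. That sentence follows the one on the primary endpoint, so for PGI-S it is context only.

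**Working it through.** **Inputs from the documents (SAP 2.2.1):** difference 1.2, SD 2.0, two-sided 5%, 45 per arm, 10% discontinuation from study drug, about 100 randomized.

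**The plan's own figure.** A two-sample t calculation (noncentral t) gives 79.5% power at 44 per arm and 80.4% at 45, so 45 reproduces. Allowing for discontinuation, 90/(1 - 0.10) = 100. This point does not dispute either number.

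**Assumptions, because the documents give no PGI-S figures:**
- Effect 1.2/2.0 = 0.6 SD, borrowed from pain.
- Week 6 to Week 12 correlation 0.5-0.8 for bias, 0.4-0.8 for precision; baseline correlation 0.3-0.5.
- Loss between Weeks 6 and 12 of 10%, borrowed from the drug-discontinuation rate.

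**Precision.** With N = 100, share m lost after Week 6 and correlation rho, the effective number for a two-visit likelihood model is N(1 - m)/(1 - rho^2 x m). The Week 12-only analysis keeps N(1 - m).
- m = 5%: 95 kept; 95/(1 - 0.008) = 95.8 to 95/(1 - 0.032) = 98.1
- m = 10%: 90 kept; 90/(1 - 0.016) = 91.5 to 90/(1 - 0.064) = 96.2
- m = 20%: 80 kept; 80/(1 - 0.032) = 82.6 to 80/(1 - 0.128) = 91.7

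**Bias without baseline adjustment.** Bivariate normal scores, 400,000 per arm, logistic loss rising with a worse Week 6 score (slope 1.5), Week 12 effect 0.6 SD:
- 10% lost in each arm: Week 12-only estimate -0.604 (true -0.604) at rho 0.5 and -0.602 (true -0.601) at rho 0.7, so no material bias.
- 5% active, 15% placebo: -0.545 (true -0.600), 0.055/0.600 = 9% too small, at rho 0.5; -0.522 (true -0.599), 0.077/0.599 = 13%, at rho 0.7.
- 15% active, 5% placebo: -0.657 (true -0.602), 9% too large, at rho 0.5; -0.673 (true -0.598), 13%, at rho 0.7.
- The two-visit estimate was within 0.002 of the true value in all six runs.

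**Bias as planned, with baseline PGI-S in the model.** A five-category scale with a baseline, 200,000 per arm, 10% lost overall, rho 0.5-0.7. Share of the true effect recovered by the planned ANCOVA:
- Worst placebo men leave, active loss random: 81-91%
- Graded loss, 5% active and 15% placebo: 92-97%
- Graded loss, 15% active and 5% placebo: 104-109%
- Same graded loss in both arms: 100-101%

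Extending the correlation to 0.8 gives a working size of about 6-9% for graded unequal loss and about 20% at most in the extreme case. The two-visit model is off by 0-3%. The result depends on how steeply loss rises with the rating: graded placebo loss with logistic slope 1 gave only about 2-4%.

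**Scale of the shift.** 6-9% of 0.6 SD is 0.036-0.054 SD, and 20% is 0.12 SD. With 45 per arm the standard error of an unadjusted difference is sqrt(2/45) = 0.21 SD, so these are roughly 0.17-0.26 and 0.57 of one standard error.

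**The case against.** The strongest reply is that little may be lost. The 10% is discontinuation of study drug, not missing Week 12 ratings. SAP 2.2.2 encourages men who stop treatment to attend later visits, including Week 12, and those who do stay in the ANCOVA. Men lost before Week 6 gain nothing from a two-visit model. Week 6 and Early Termination ratings are still summarized descriptively, so such men do not vanish from the report. Secondary P values are descriptive. All of this stands and keeps the point at low severity.

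A second reply is that the simulations favour MMRM, because loss was made to depend only on the observed Week 6 score. That is fair. When loss at 10% depended on the Week 12 value itself, the two-visit model recovered about 75-88% of the effect: better than the ANCOVA, but not a cure.

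A third is that the SAP consistently gives its categorical endpoints single-visit tests. This has less force for PGI-S, because the SAP already models its change as a number. Protocol 10.4.2.5 planned a CMH test for PGI-S, so the step from categorical to numeric has been taken.

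A reader might infer that GRA and PGI-C need the same change. The documents do not support that. Neither scale has a baseline, so the baseline and baseline x visit terms of SAP 2.2.13.1 cannot be fitted, and replacing a planned ordinal score test with a normal model is debatable. A reader might also infer that the meaningful-change threshold is compromised, since PGI-S and PGI-C are its anchors. SAP 2.2.13.3 says the threshold is determined outside the SAP's methods, from data of both arms; the PGI-S treatment test does not feed it.

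**Conclusion.** The point holds for PGI-S as a cheap improvement of low severity. The planned ANCOVA omits men with a Week 6 but no Week 12 rating, and the SAP already has a model that would use them. Under the stated assumptions, bias is about 6-9% in either direction when graded loss differs by arm, up to about 20% in the extreme case, and about zero when loss is equal. At 10% loss, effective N rises from 90 to about 91.5-96 of 100.

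A reader might infer a bias of 15-26%. That size needs the worst 10% of placebo men to leave while active loss is random, and it ignores the baseline PGI-S covariate in the planned model. A reader might also call this a completer analysis; it is an observed-case analysis, since men off drug who attend Week 12 are included.

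The conclusion rests on a loss rate, correlations and an effect size that the documents do not give for PGI-S. The MMRM removes the bias only if loss depends on observed ratings. The primary analysis is untouched.

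**What to change.** In SAP 2.2.13.3, replace the Week 12 PGI-S ANCOVA with the model of SAP 2.2.13.1: change from baseline at Weeks 6 and 12, with baseline PGI-S, treatment, visit, baseline x visit and treatment x visit, and unstructured covariance. Report the Week 12 LS-mean difference with its 95% CI. Keep the Week 12 frequency table.

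Leave the planned Week 12 row-mean-score test for GRA and PGI-C. A two-visit model without own-baseline terms could be added as a supportive analysis, but is optional. Tabulating by arm the number of men with a Week 6 but no Week 12 PGI-S would show whether the issue mattered.

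The cost is a few lines of SAP wording and reuse of the Appendix B primary-endpoint program, with no new data and no extra patients. The trade-off is reliance on a missing-at-random assumption, which the SAP already makes for its primary MMRM.
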